6. SPECIFIC AIMS

Study Primary Objective: To compare adherence to fixed dose TDF/FTC, as measured by intracellular levels of TFV-DP \geq 1246 fmol/punch, between subjects randomized to receive iTAB with versus without brief Motivational Interviewing, when used for adherence support to pre-exposure prophylaxis among transgender / gender non-conforming (TG / GNC) individuals at elevated risk for HIV acquisition.

Hypothesis: Subjects randomized to the iTAB intervention plus MI-b will have higher adherence, as measured by intracellular levels of TFV-DP ≥ 1246 fmol/punch, at both week 12 and their last visit after week 12 up until 48 weeks (eg week 24, 36 or 48), compared to those with iTAB alone in those that complete those visits and have a measureable level. To be considered adherent they must have attended the week 12 visit; if week 12 was attended but was the last visit, then only the week 12 visit will be required for the endpoint.

Study Secondary Objectives

To compare adherence to fixed dose TDF/FTC, as measured by intracellular levels of TFV-DP ≥ 719 fmol/punch, between subjects randomized to receive iTAB with versus without brief Motivational Interviewing, when used for adherence support to pre-exposure prophylaxis among transgender / gender non-conforming individuals at elevated risk for HIV acquisition.

Hypothesis: Subjects randomized to the iTAB intervention plus MI-b will have higher adherence as measured by intracellular levels of TFV-DP \geq 719 fmol/punch, at both week 12 and their last visit after week 12 up until 48 weeks (eg week 24, 36 or 48), compared to those with iTAB alone in those that complete those visits and have a measureable level. To be considered adherent they must have attended week 12 visit; if week 12 was attended but was the last visit then only the week 12 visit will be required for the endpoint.

- 2. To compare adherence to TDF/FTC in the iTAB+MI-b versus iTAB alone arms using
 - a) a continuous outcome of DBS TFV-DP drug levels at weeks 12 and 48 in participants who attended both visits
 - b) TFV-DP intracellular levels of ≥ 1246 fmol/punch and ≥ 719 fmol/punch at both week 12 and week 48
 - c) a stratified analysis of drug level outcomes within male-assigned at birth and female-assigned at birth groups
 - d) a composite endpoint with the outcome defined as "all attended visits (regardless if they missed week 12)" with levels of \geq 1246 fmol/punch and \geq 719 fmol/punch.

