- 3. To compare self-reported adherence to TDF/FTC in the iTAB+MI-B versus iTAB arms over 48 weeks using
 - a) adherence defined as "the proportion of text-reported doses over all possible doses over 48 weeks"; missing text messages or early discontinuation of the study will be considered as no doses taken
 - b) a continuous measure of the percentage of days adherent by self reported measures (iTAB, cumulative 3 day recall, and the visual analog scale) in an "as treated" analysis for those that are retained on study
- c) stratified analysis of 3a and 3b outcomes within male-assigned at birth and female-assigned at birth groups
- 4. To compare study retention between arms, defined as the proportion of participants that complete all study visits regardless of whether they were on drug or not
- 5. To determine factors associated with poor adherence (< 719 fmol/punch over 48 weeks) and discontinuation of TDF/FTC
 - Factors considered to be associated with poor adherence to TDF/FTC will include demographics, socioeconomic status, perception of HIV risk, ongoing substance use, intimate partner violence, low health/HIV and health systems literacy, and stigma
- 6. To determine the rate of linkage and continuation of TDF/FTC at 12 weeks after study completion between arms
- 7. To determine the rate of HIV seroconversion in TDF/FTC-using transgender / gender non-confirming individuals and compare the proportion of seroconversions over 48 weeks between arms
- 8. To measure the acquisition of other sexually transmitted infections (STIs) and compare rates of acquisition of new STIs at any site between arms
- 9. To evaluate changes in risk behavior after PrEP initiation (risk compensation) by comparing the numbers of HIV positive partners, partners of unknown HIV status, unprotected insertive and receptive anal or vaginal acts between Baseline and subsequent visits
- 10. To evaluate the safety and tolerability of daily TDF/FTC as PrEP as measured by discontinuations due to
 - a) any adverse events
 - b) serious adverse events and
 - c) grade 2 or higher adverse events

Sub-study I Primary Objective: To determine whether csHT interacts with PrEP in male-assigned at birth (MAAB) persons that would affect efficacy of PrEP, measured by intracellular TDF concentrations in DBS.

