9. RESEARCH DESIGN AND METHODS

STUDY DESIGN

CCTG 603 is an open-label, two-arm, randomized (1:1) clinical demonstration project to determine if brief Motivational Interviewing (MI-b) added to a text message-based adherence intervention (iTAB) improves adherence to PrEP among transgender / gender non-conforming persons.

Site Initiation

Before implementing this protocol, sites must be registered with and approved by the CCTG Core to initiate, and must have the protocol and informed consent form approved by the local institutional review board (IRB).

Screening Visit (approximately 1-2 hours)

Screening occurs prior to the participant completing any assessment or taking any study medications, treatments, or interventions. The Screening Visit and study enrollment may only be initiated in-person; to enroll, a participant must present to one of the clinical site facilities.

Registration Prior to the Screening Visit

Each participant will be assigned a patient identification number (PID) and a study identification number (SID). Both PIDs and SIDs must be included on every source document and laboratory sample for that participant. Each site is responsible for maintaining a master list of PIDs and SIDs in a central location.

- PIDs will be generated automatically by the study's Electronic Data Capture (EDC) system upon participant registration. Each unique person will be assigned only one PID that will be used across all studies; if a person has been assigned a PID from a previous study, a new PID will not be generated.
- SIDs will be assigned using the site's SID Assignment List and will be used for that study only. SIDs will not be reassigned should a participant screen fail, withdraws from the study, or ultimately does not provide written consent.

During the Screening Visit

All participants interested in screening for CCTG 603 will sign an Informed Consent Form (ICF) that had been approved by a site's local IRB.

Screening procedures will include:

- Assessment of inclusion and exclusion criteria
 - Confirmation of HIV status and screening for acute HIV symptoms using NAT or equivalent test (antigen/antibody).
- Laboratory evaluations
 - HBsAg
 - Calculated creatinine clearance (Cockcroft-Gault)
 - Urinalysis
 - o Urine for β-HCG performed for participants capable of becoming pregnant.
 - Laboratories obtained as part of regular clinical care may be used to satisfy screening evaluations.

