The primary endpoint will be a composite adherence outcome determined by dried blood spot intracellular tenofovir diphosphate (TFV-DP) levels. A subject will be considered adherent if the TFV-DP levels are above 1246 fmol/punch (consistent with 7 doses in past week) at both week 12 and the last study visit over the 48 weeks. All randomized subjects that were dispensed PrEP at baseline will be included in the modified intent-to-treat analysis. Participants not achieving week 12 will be considered non-adherent.

Secondary Adherence Endpoints

A key secondary endpoint will be a composite outcome determined by TFV-DP levels at both week 12 and the last study visit associated with adequate adherence (>719 fmol/punch).

Self-reported adherence to PrEP through 48 weeks is defined as the proportion of text-reported doses over all possible doses in 48 weeks. Missing responses due to either missed text messages or early discontinuation of the study will be considered as no doses taken. Sensitivity analysis will also be done on the 'as-treated' population (i.e. treat missing as missing).

Additional self-reported adherence measure will be >90% adherence (i.e. on the ACTG 4-day recall at weeks 12, 24, 36, and 48); >90% dosing by VAS at each study visit.

- Poor adherence is defined as < 4 doses a week or discontinuation of study drugs. Subgroup analysis will explore the endpoint for discontinuation for reasons other than lack of risk or confirmed adverse event.
- Safety and tolerability outcomes are defined as incidence rates of: i) discontinuation of TDF/ FTC for any toxicity; ii) grade 2 or higher adverse event (symptoms or laboratory toxicity); iii) serious adverse events; iv) death

Randomization and Stratification

Subjects will be randomized (1:1) to one of two arms: the **iTAB** or the **iTAB+MI-B** enhanced adherence arm. Randomization will be stratified by clinic site, sex assigned at birth (male vs female), and prior history of PrEP use. Participants assigned "intersex" at birth will be included in the female group. A total of 300 subjects (150 per arm) will be randomized and followed in the study for 48 weeks after enrollment of the last subject.

Once eligibility and consent are confirmed, randomization will occur using the web-based CCTG data management system.

Study Power and Sample Size Justification

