The study is powered to compare the primary adherence rate between the two study arms using a two-sample, two-sided proportion test. Expected drug-level adherence based on a previous study of MSM using iTAB for PrEP for this composite endpoint (>=1246) was 33%. Assuming the adherence rate of the transgender iTAB alone group will be the same the study has 77% power to detect a difference of 16% between the iTAB+MI group and the iTAB alone group, with 150 subjects per group.

Monitoring

The study team will review all adverse events during PrEP therapy as cumulative reports in both arms combined, on monthly team calls. Adverse events will be graded using the ACTG toxicity grading scale and recorded using standard CCTG AE electronic data capture. An independent Data Safety and Monitoring Board (DSMB) will not be used for this study because the drugs are licensed for this indication and relatively non-toxic.

Statistical Analysis Plan

In general, analyses of efficacy will incorporate the modified intent-to-treat (mITT) principle, namely, all randomized participants dispensed study medication will be included in the analysis. For all secondary analyses of efficacy, no adjustments for multiple comparisons will be made and a p-value of 0.05 will be considered statistically significant. Analyses of safety will be focused on "as treated" populations.

Demographic and baseline measurement variables will be summarized via standard descriptive statistics. There will be no interim analyses for futility or efficacy conducted.

Analysis of Primary Outcome

Descriptive analysis will be performed on the primary adherence outcome via a frequency table and Fisher's exact test. Logistic regression modeling will be conducted to assess the group differences while adjusting for potential covariates.

Analysis of additional Secondary outcomes

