Descriptive analysis will be performed for all the secondary outcomes. For comparisons between the two study arms, Fisher's exact test will be used for categorical outcomes; t-test or Wilcoxon rank sum test will be used for continuous outcomes. Multivariable logistic regression model will be used to study factors associated with poor adherence. Factors will include demographics, substance use, untreated mental illness, socieconomic status, low health/HIV and system literacy, fear of disclosure and non-English language. To evaluate changes in risk behavior after initiation of PrEP, descriptive summary will be provided for the number of HIV positive/unknown status partners and any unprotected anal intercourse with an HIV positive/unknown status partner by visit (at w12, 24, 36 and 48). Wilcoxon signed rank test will be used for comparison at each follow-up visit to the baseline visit. GEE model will be used to assess the change in risk behavior over time.

Safety analysis

Safety data will be reported for all the randomized subjects while they were taking or immediately (30 days) after taking study drug (as treated analysis). Tables will summarize the number of serious adverse events, adverse events (grade 2 or higher), PrEP discontinuation due to adverse events, by study arms and overall. Fisher's exact test will be used to compare the rates between the two groups. The time to TDF/FTC discontinuation due to adverse events will be compared between groups using the log-rank test and plotted using Kaplan-Meier curves.

SUB-STUDY I DESIGN

This pharmacologic sub-study will use the main study cohort to determine the interaction of cross-sex hormone therapy (csHT) on PrEP efficacy as measured by TFV-DP and FTC-TP DBS intracellular levels, and of PrEP on csHT effectiveness as measured by quantitative hormone levels in plasma.

SUB-STUDY I PROCEDURES

Subjects will be consented for participation in the sub-study at the main study's Screening Visit.

As part of the main study, plasma and DBS samples will be collected at Baseline and every 12 weeks. A Baseline DBS sample will be collected only if the subject is already on PrEP at the time of Baseline. Detailed concomitant hormone use, including route and frequency, will be collected at every clinic visit. Daily iTab responses will be used as a self-reported adherence measure.

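### No main-study comparison of the arms is adjusted by name for the randomization strata; naming one strata-adjusted primary analysis would cost nothing and may add power

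*Combined protocol and SAP*

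**What the plan says.** Section 9 of the combined protocol and SAP, Randomization and Stratification: "Randomization will be stratified by clinic site, sex assigned at birth (male vs female), and prior history of PrEP use". Participants recorded as intersex at birth are grouped with female.

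Three passages in section 9 bear on the primary comparison:

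- Study Power and Sample Size Justification, first sentence: "The study is powered to compare the primary adherence rate between the two study arms using a two-sample, two-sided proportion test".
- Analysis of Primary Outcome, first sentence: "Descriptive analysis will be performed on the primary adherence outcome via a frequency table and Fisher's exact test".
- Analysis of Primary Outcome, second sentence: "Logistic regression modeling will be conducted to assess the group differences while adjusting for potential covariates".

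For secondary comparisons between arms, "Fisher's exact test will be used for categorical outcomes; t-test or Wilcoxon rank sum test will be used for continuous outcomes". Safety comparisons use Fisher's test and the log-rank test, with no strata mentioned.

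Sex assigned at birth returns only in secondary objectives 2c, "a stratified analysis of drug level outcomes within male-assigned at birth and female-assigned at birth groups", and 3c, "stratified analysis of 3a and 3b outcomes within male-assigned at birth and female-assigned at birth groups". Both are analyses within each sex group, not adjusted comparisons of the arms. Stratification variables are named as model terms only in the Sub-study I sensitivity regression, which compares male-assigned-at-birth participants with existing MSM data.

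Section 9, Statistical Considerations, leaves detail to a formal SAP due before database lock. That SAP is not in the text supplied.

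**The concern.** When randomization is stratified on factors that predict the outcome, the arms are balanced on those factors by design. An analysis that ignores them still uses a standard error computed as if they could be unbalanced, so it is conservative and gives up power. Fisher's exact test adds a conservatism of its own. Adjusting for the strata recovers both losses with data already in hand.

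The text also leaves open which analysis is primary: the proportion test of the power sentence, Fisher's test or the logistic model. The power sentence points to an unadjusted test, but nothing labels it so. The covariates of the logistic model are not listed. Since "CCTG 603 is an open-label, two-arm, randomized (1:1) clinical demonstration project", database lock alone does not guarantee that the list is fixed before anyone can see outcomes by arm.

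At stake are a few points of power in a trial that states 77%, and a primary model fixed in advance.

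**Working it through.** **Inputs from the documents.** 150 per arm; 33% adherent with iTAB alone; a difference of 16 points, so 49%; two-sided test; five sites; 280 of 300 expected to be male-assigned at birth. Alpha of 0.05 is stated only for secondary efficacy analyses and is assumed here for the primary.

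**Step 1: the stated power.** The standard error under the alternative is √[(0.33×0.67 + 0.49×0.51)/150] = 0.0560. Under the null, with pooled rate 0.41, it is √[2×0.41×0.59/150] = 0.0568.

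- Without continuity correction: Φ[(0.16 − 1.96×0.0568)/0.0560] = 80.8%.
- With continuity correction (subtract 1/150 from the difference): 77.3%, which reproduces the stated 77%.
- Exact enumeration: Fisher 78.1%, chi-square 81.4%.

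**Step 2: size of the unadjusted tests.** These are exact values at 150 per arm.

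| Common rate | Fisher | Chi-square |
|---|---|---|
| 33% | 3.75% | 4.95% |
| 37% | 3.72% | 4.93% |
| 41% | 3.98% | 5.26% |

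**Step 3: simulated power at 33% versus 49%.** There were 20,000 runs per scenario (Monte Carlo standard error 0.3 point for power, 0.15 for size). Assumptions not in the documents: five sites of 60, prior PrEP use 30%, stratified blocks of 4, no effect of sex. The prior-PrEP odds ratio and the range of site odds ratios were: none; mild 1.5 and 0.67–1.5; moderate 2 and 0.5–2; strong 4 and 1/3–3. The adjusted analysis is the standardized risk difference from a logistic model with main effects for the three factors.

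| Strata | Fisher | Chi-square | Adjusted | Adjusted − Fisher | Adjusted − chi-square |
|---|---|---|---|---|---|
| None | 80.1 | 81.6 | 81.6 | 1.5 | 0.0 |
| Mild | 79.7 | 81.3 | 82.2 | 2.5 | 0.9 |
| Moderate | 80.6 | 82.2 | 84.0 | 3.4 | 1.8 |
| Strong | 81.8 | 83.5 | 88.2 | 6.4 | 4.7 |

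The difference between the last two columns, 1.5 to 1.7 points, is the gain from leaving Fisher's test. At exactly 150/150 that gap is 81.4 − 78.1 = 3.3 points; it is smaller in simulation because incomplete blocks vary the arm totals.

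**Step 4: simulated size at a common rate of 41%** (none, mild, moderate, strong). Fisher: 4.5, 4.0, 3.8, 2.7%. Adjusted: 5.3, 4.9, 5.2, 5.1%.

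**Step 5: precision.** The mean standard error of the unadjusted risk difference is 0.0559 (0.0558 in the moderate runs). Adjusted, it is 0.0560, 0.0553, 0.0539 and 0.0508. In the strong case the variance falls by 1 − (0.0508/0.0559)² = 17%; in the moderate case, by 1 − (0.0539/0.0558)² = 7%.

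**Step 6: sensitivity.**

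- *Other stratum effects, including sex* (4,000 runs; sex odds ratio 0.67 moderate, 0.5 strong; prior-PrEP odds ratio 1.5 and 3; site standard deviation 0.3 and 0.6 on the logit scale). Fisher versus adjusted logistic: 79.4/81.6 (none), 80.6/83.4 (moderate), 81.6/86.7 (strong).
- *Prior PrEP use of 10% or 50%*, moderate effects: total gain over Fisher 3.3 or 3.6 points.
- *Unequal sites* (110, 80, 70, 30, 10), moderate effects, 10,000 runs: Fisher 79.9, adjusted 83.7, adjusted size 5.2%. With the 10-person site merged: 80.9, 84.4 and 5.1%. Fits with an extreme coefficient fell from 34 to 1 in 20,000.

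**The case against.** The strongest case against is that little may be missing. A covariate-adjusted logistic regression is already planned, the section describes itself as brief, and the formal SAP has precedence. The Sub-study I regression shows that the team thinks of strata as covariates. If the SAP lists them, all that remains is to label the adjusted model primary. This stands as a limit on weight. But nothing supplied names the strata for a comparison of the randomized arms, and the Sub-study I model is not such a comparison.

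Second, gains measured against Fisher's test overstate what the strata contribute. Against an uncorrected proportion test the gain is 0 to about 2 points under the null to moderate assumptions. That is right, and the two parts are shown separately above.

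Third, the stratum effects are invented. This also stands: the range starts at no effect, and the strong case is an illustrative upper end, not an expectation.

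Fourth, not every strata-adjusted test helps. In the second set of scenarios, a continuity-corrected Cochran–Mantel–Haenszel test over 20 cells gave 76.5% and 78.6% (none, moderate), below Fisher's 79.4% and 80.6%. The sparse cells follow from about 20 participants not male-assigned at birth. The method must therefore be named; a main-effects model avoids this loss.

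Finally, the endpoint is a laboratory level, no interim efficacy analysis is planned, and adverse events are reviewed with arms combined. Nothing suggests that outcomes by arm will be examined early. The open-label design is a reason to date the choice, not evidence of a problem.

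**Conclusion.** The point holds as an optional improvement. No main-study comparison of the arms names the factors on which randomization is stratified, and no analysis is designated as primary. The plan is valid as it stands: the unadjusted test is conservative rather than biased, and its power is about what is stated.

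A main-effects adjusted analysis keeps size near 5% and gains between 1.5 and 6.4 points of power over Fisher's test at the same sample size. The part due to the strata themselves is 0 to 4.7 points, and about 2 or less unless they are strongly prognostic. These figures rest on assumed stratum effects, prior-PrEP prevalence, site sizes and block size. The direction does not depend on them: in no scenario run did this model have lower power than Fisher's test.

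**What to change.** State the following in Analysis of Primary Outcome and in the SAP, dated before outcome data by arm are reviewed:

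> The primary analysis is a logistic regression of the composite adherence endpoint on arm, with site, sex assigned at birth (as randomized, intersex grouped with female) and prior PrEP use as main effects, in the mITT population. The primary estimand is the standardized risk difference from this model. The two-sided p-value (alpha 0.05) and the 95% confidence interval both come from this estimate and its robust standard error. Any site with fewer than 15 mITT participants, arms pooled, is merged with the next smallest site. Fisher's exact test, the adjusted odds ratio and models with further pre-listed covariates are supportive.

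The risk difference is on the scale of the power statement. The adjusted odds ratio with its own p-value and interval would serve equally; what matters is one estimand for both. In the simulations, an odds-ratio p-value paired with a risk-difference interval gave opposite verdicts in 0.03–0.20% of trials. The threshold of 15 is an example; it needs only to be fixed in advance.

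The cost is a few sentences. The three variables are recorded at randomization, and no participants, visits or assays are added.

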- Ability to access and maintain their PrEP regimen since EOS
- Ability to access health insurance coverage since EOS
- If participant has not accessed PrEP and/or does not have health insurance, the participant will be asked for their reasons and possible barriers to uptake
- Adherence (if on PrEP)
- HIV risk behavior
- Perceptions of PrEP efficacy

Schedule of Evaluations for Subjects On-study, Off-medications

At any point of the study, participants may elect to stop study medication but remain on study. Participants not on study medication will follow the same schedule as defined in the schedule of evaluations until the end of study, with the following exceptions:

- Medication will not be dispensed
- Adherence counseling and monitoring of medications will not be performed
- DBS will not be collected
- iTAB account for participant will be switched to "inactive"

		Study Weeks of Follow-up								Interim ⁷	
Schedule of Evaluations	Screen	Wk 0	Same-day PrEP	2	12, 24, 36	48 / EOS	48 EXT ◊	60	Visit	Phone	
Window		30 days		+/- 1 week	+/- 4 weeks			+/- 4 weeks			
Informed Consent	Χ		Х								
Inclusion / Exclusion	Χ		Х								
Randomization		Χ	Х								
iTAB setup		Χ	X								

Medical/medication										1
history and targeted	Χ	Х	X		X	X	X		Χ	
physical exam										
HIV risk reduction		X	Х		Х		X			
counseling										
Adherence counseling ¹		Χ	X		X		Х			
TFV/FTC dispensed ¹		X	Χ		Х		Х		(X)	
Telephone follow-up				Χ				X		Χ
Adverse events				Х	Х	Х			(X)	(X)
assessment ¹				,,	^	^			(71)	(71)
Computer assisted self-	Х	Х	X		Х	Х				
interview (CASI) surveys	,,	,								
End of Study survey						Х				
Post-study survey						 		Χ		
Laboratory										
HIV EIA / NAT or Ag/Ab	Х		Х		(X) ²		(X) ²		(X) ²	
test					(^)		(^)		(^)	
HBsAg	Χ		X							
Creatinine and GFR	Х		X		Х	X	X			
(calculated CrCl) ¹					^	^	^			
Urinalysis	X		X							
Urine β-HCG ³	X	Χ	Х		X	X			(X)	
CBC, liver enzymes		Х	Х							
Rapid HIV		Х	Х		X	X	X		(X)	
STI screen [†] : GC, CT,		X	Х		X ⁵	X			(X)	
syphilis		^	^		Λ	^			` ,	
GC Treatment [†]									(X)	
Plasma hormone levels ⁴		Χ	Х		(X)					
Dried Blood Spot (DBS) ¹		(X) ⁶	(X) ⁶		X	X			(X)	
Banked whole blood,		Х	Х		Х	Х				1
serum, plasma										
Banked urine		Χ	X		X	X				
Banked rectal swabs		Х	Х			Х				
(x2)		^	^			^				
HIV confirmatory test if	(X)		Х		(X)	(X)	(X)	(X)	(X)	
HIV+	(//)				(//)	(//)	(//)	(//)	(//)	
CD4, HIV RNA, and HIV										
genotype if HIV+ after			Χ		(X)	(X)	(X)	(X)	(X)	
baseline										

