¹ Only for participants curre	ently taking	n PrFP Pai	rticinants red	uirina PrFI	P dispensation dur	ing an Interi	m visit v	vill rece	ive enou	ah PrFP

Only for participants currently taking PrEP. Participants requiring PrEP dispensation during an Interim visit will receive enough PrEP to last until the next regular study visit.

Adherence and Behavioral Assessments

We will measure adherence using the self-report daily text messages. These texts will include a personalized lead-in reminder message (e.g., "Those who are closest to you care about your health") and participants will be asked "Did you take your dose today? Reply: Y) Yes N) No P) Postpone". If 'Postpone' is selected, participants will receive a follow-up message 1 hour later asking them if they took their medication (Yes or No). Participants will also have the option of determining the word used to describe the study drug (e.g., 'med', 'dose', or other personal choice). Nonresponse or a 'No' response will be counted as not taking their dose. At each follow-up

² Participants with medication interruption greater than 14 days will require confirmation of HIV seronegative status prior to re-initiation of PrEP. Re-initiation must be achieved prior to the end of the week 36 visit.

³ Only for participants capable of becoming pregnant

⁴ Only for participants currently taking csHT. Baseline and Week 12 only.

⁵ STI screen only at week 24

⁶ Week 0 DBS collected only if participant is already taking PrEP at Baseline

⁷ Interim visit for: HIV testing if off PrEP for over 1 week and had high risk event, consider NAT or Ab/Ag; STI testing only if has symptoms (urethral discharge, genital sore); if seroconverted outside study; adverse event assessment

[†] UCSD-only sub-study evaluation. Additional specimens will be collected from anatomic site of positive GC at time of treatment. ♦ UCSD-only study extension

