For security measures, the database is password protected, fully encrypted and only accessible by the Data Manager. Data management for this study will be provided through the Open Source Clinical Content Management System (OCCAMS) developed by the CCTG Data Core. OCCAMS provides integrated, flexible, and secure tools for complex clinical study data management using only a web browser. The Data Core ensures data security though a robust security model consisting of a multi-level hardware/software firewalled network, secure hardware and software encryption, data auditing and access tracking procedures, and completely redundant services hosted from two physically separated server facilities. Therefore the input and extraction of this data is only done by personnel with appropriate access to the system. Study personnel will use OCCAMS from a web browser to manage all data storage, quality control, and retrieval. Each staff member will be provided a login and password and will be assigned to the appropriate role-based groups using the UCSD campus active directory. Membership in these role-based groups will provide users with the necessary web views to complete their assigned tasks on a need to know basis. Information from the database will only be shared with the research team. The research team includes the researchers and people hired by the University or an outside company who contracts with the University to sponsor the research activities being done at the AVRC.

STATISTICAL CONSIDERATIONS

A formal Statistical Analysis Plan (SAP) will be drafted and finalized prior to database lock. The SAP will contain a more detailed and/or comprehensive presentation of statistical methods; attention to any changes of substance to planned analysis procedures relative to those indicated in the protocol will be submitted as an amendment. The SAP is the final authority for all statistical analyses. The following section briefly describes the planned statistical analyses. In case the language in this section differs from the language in the SAP, the SAP takes precedence.

Primary Endpoints

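### If stops for other reasons are censored, the planned Kaplan-Meier plot of stopping TDF/FTC for adverse events reads somewhat above the proportion who actually stop for them; a cumulative incidence curve avoids the question.

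*Combined protocol and SAP*

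**What the plan says.** The Safety analysis paragraph (section 9, Statistical Considerations) reports safety data for randomized subjects "while they were taking or immediately (30 days) after taking study drug (as treated analysis". Tables will give "PrEP discontinuation due to adverse events, by study arms and overall", with Fisher's exact test between arms. The paragraph then adds: "The time to TDF/FTC discontinuation due to adverse events will be compared between groups using the log-rank test and plotted using Kaplan-Meier curves".

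The part of section 9 on subjects who are on study but off medication says that "participants may elect to stop study medication but remain on study", and that "Participants not on study medication will follow the same schedule as defined in the schedule of evaluations until the end of study", with listed exceptions. Footnote 1 to the Schedule of Evaluations limits AE assessment to participants currently taking PrEP. Footnote 2 covers interruptions of more than 14 days, requires a confirmed HIV-negative result before restart, and adds: "Re-initiation must be achieved prior to the end of the week 36 visit".

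No section says how a stop for a reason other than an AE enters the time-to-event analysis, and no competing-risk method is named. The opening of Statistical Considerations defers detail: "A formal Statistical Analysis Plan (SAP) will be drafted and finalized prior to database lock".

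**The concern.** A participant who has stopped TDF/FTC for good for another reason can no longer stop it because of toxicity. Censoring that participant treats them as still able to have the event later, with the same hazard as those who remain on drug. One minus Kaplan-Meier then estimates the risk in a setting without other stops, and only if those stops are independent of AE risk. It does not estimate the proportion of participants dispensed drug who stop for AEs.

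Secondary objective 10 (section 6) measures safety and tolerability by discontinuations due to AEs, so readers are likely to take a week-48 toxicity figure from this plot. Under censoring, that figure would be too high as a description of what happened to the cohort.

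**Working it through.** The plan gives no figure for this analysis, so there is none to reproduce. It also gives no rate of stopping for AEs or for other reasons; every rate below is an assumption, shown as a range.

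**Inputs.** From the documents: 150 per arm (Randomization and Stratification), 48 weeks on drug (section 4), and a safety window of drug time plus 30 days (Safety analysis). Assumed: *a*, the true proportion who stop for AEs by week 48, and *b*, the proportion who stop permanently for other reasons.

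**Reading 1: other stops are censored at the stop.** With constant hazards, the total cumulative hazard is L = −ln(1 − a − b), the AE share is L·a/(a + b), and the curve reads 1 − exp(−L·a/(a + b)).

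- a = 0.03, b = 0.10: L = −ln(0.87) = 0.1393; AE share 0.1393 × 3/13 = 0.0321; the curve reads 3.16%.
- a = 0.03, b = 0.40: L = −ln(0.57) = 0.5621; AE share 0.5621 × 3/43 = 0.0392; the curve reads 3.85%.

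**Variant: censored 30 days after the stop.** The AE density a·L·exp(−Lt/48)/[48(a + b)] is divided by a risk set that also holds those who stopped for other reasons in the last 30 days. This is integrated numerically over 48 weeks.

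**Timing bounds.** If all other stops come after the AE stops, the curve reads *a* (no bias). If all come before, it reads a/(1 − b).

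Results for a true 3%:

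| Other stops, b | Censored at stop | Censored 30 days later | Upper bound a/(1 − b) |
|---|---|---|---|
| 10% | 3.16% | 3.13% | 3.33% |
| 20% | 3.35% | 3.29% | 3.75% |
| 30% | 3.58% | 3.47% | 4.29% |
| 40% | 3.85% | 3.68% | 5.00% |

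The constant-hazard excess is 0.2 to 0.9 points, or about 0.2 to 1.3 participants of 150. The standard error per arm is √(0.03 × 0.97/150) = 1.4 points. In this table only the 5.00% bound, 2.0 points high, exceeds it.

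**Other assumed AE rates, constant hazards, b from 10% to 40%.**

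- True 1%: 1.05% to 1.28% (standard error 0.8 points).
- True 5%: 5.27% to 6.43% (standard error 1.8 points).
- True 10%: 10.6% to 12.9% (standard error √(0.10 × 0.90/150) = 2.4 points). Here the top of the range, 2.9 points high, passes one standard error.

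**Reading 2: other stoppers stay in the risk set, event-free, to week 48.** With complete follow-up, one minus Kaplan-Meier equals *a*, so the excess is zero.

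**Simulation check.** In 2,000 simulated arms of 150, with 5% AE stops and 30% other stops, the mean week-48 readings were 6.0% (censored at stop), 5.8% (censored 30 days later), 5.0% (kept at risk) and 5.0% (Aalen-Johansen). Adding 10% loss to follow-up gave 6.1%, 5.9%, 5.1% and 5.1%.

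**The case against.** The strongest reply is that no written rule is wrong. The section describes itself as brief and leaves detail to the SAP, and one of the two readings has no bias. That stands: a reader might infer that the plan prescribes censoring, but it does not. The drug-plus-30-days window and footnote 1 lean that way, while continued visits off drug make the other reading possible.

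Second, high depends on the target. For toxicity while exposed, and if other stops are independent of AE risk, the censored curve has a legitimate meaning. That also stands. The excess is relative to the proportion of participants dispensed drug who stop for AEs, and the plan should say which quantity it wants.

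Third, the by-arm table already gives the crude proportion, and a sentence keeping other stoppers at risk would repair the Kaplan-Meier plot about as well. Both are true. They limit the weight of the point, but they do not argue for leaving the rule unstated.

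A reader might also infer that the safety comparison is invalid. It is not. With other stops censored, the log-rank test compares cause-specific hazards, and Fisher's exact test does not use the curve.

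Finally, footnote 2 might be taken to define a permanent stop. It does not: it sets a restart deadline for interruptions of more than 14 days. Read as a definition, it would make even a few missed days after week 36 permanent.

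**Conclusion.** The point holds conditionally and is small. If non-AE stops are censored, the plotted curve overstates the proportion who stop for AEs: 3.2% to 3.9% against a true 3%, under assumed other stops of 10% to 40% and constant hazards. That is within one standard error. Larger excesses need other stops concentrated early, or higher AE stopping than the central assumption. If other stoppers are kept at risk with complete follow-up, the excess is zero.

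Only one secondary safety figure is affected, and no test or conclusion in the plan changes. The excess would differ between arms only if non-AE stopping did, and the documents give no data on that. It merits correction because under censoring the error always runs upward and is easily avoided.

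**What to change.** Keep the log-rank test and the by-arm table. Replace the Kaplan-Meier plot with Aalen-Johansen cumulative incidence curves by arm, with non-AE discontinuation and death as competing events. The SAP should state four things:

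- **Target:** the proportion of participants dispensed drug who stop for AEs.
- **Discontinuation:** the SAP's own definition, for example an interruption of more than 14 days with no restart by last contact or week 48. This is consistent with footnote 2 but not taken from it.
- **Loss after an elective stop:** a competing event at the stop date.
- **Censoring:** only loss to follow-up while on drug.

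With complete follow-up this curve equals the Kaplan-Meier curve that keeps other stoppers at risk, so nothing is lost if that was the intent. Since "There will be no interim analyses for futility or efficacy conducted", stops can be classified once, before database lock.

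The cost is a short SAP entry and a standard software routine. Stop reasons and restarts must be coded. The Secondary Adherence Endpoints text already needs the reasons, for its subgroup analysis of discontinuation other than for lack of risk or a confirmed AE. The curve may differ slightly from the crude table if participants are lost while on drug.
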